### 7.5.2 Interim feasibility assessment

An interim assessment to determine the feasibility of continuing the pregnancy registry will be conducted by the Sponsor at the end of three years from the start of the Registry and detailed in the separate SAP. At this interim assessment, data from the following sources will be examined in an integrated manner to determine the feasibility of continuing the pregnancy registry:

- Data from the Registry informing participant demographics (age distribution) and enrollment rate
- Data from secondary analysis of US real world data sources (such as Truven Health MarketScan) informing number and characteristics (age) of siponimod female patients, number of siponimod exposed pregnancies and live birth rate,
- Aggregate US marketing data informing the number and age distribution of US siponimod-exposed women
- Data from PRegnancy outcomes Intensive Monitoring program (PRIM – based on worldwide spontaneous reporting) informing number of pregnancies and outcomes from all over the world including US (for those reports that are not enrolled in the registry)
- Change in treatment landscape with availability of newly marketed drugs safer to use in pregnancy affecting the uptake of siponimod in women of child bearing potential

The integrated analysis of all these data will provide a basis for understanding the siponimod female patient population's characteristics and will help assess whether the scientific question of interest is at all relevant for the siponimod population and whether the Registry will be able

to answer the question in a reasonable timeframe (i.e. study results with targeted sample size with seven years of enrollment).

## **7.6 Data management**

Data will be collected using maternal interview(s), medical records, pregnancy exposure diary, dysmorphology examination data, and ASQ data. Maternal interviews, pregnancy exposure diary, and dysmorphology examination data will be recorded on hard copies of forms and these records will be retained by OTIS. These forms are considered the primary data sources for the study. Medical records and ASQ will be received on hard copy forms or electronically. Data from these forms will be extracted and entered into a customized OTIS study database located in the Research Center and developed specifically for the OTIS studies.

The database itself has built in range limits for key variables that prevent certain data entry errors. In addition, all data entry forms will be reviewed for logical errors by the study data manager on a regular basis and 100% of key variables are double-checked for data entry accuracy. The study statistician also conducts reviews of the cumulative data from the study in the database for distributions and values that are illogical. The study manager will be responsible for working with the data manager and the supervisory staff to oversee the data validation procedures.

Access to the database will be controlled by password, with different access privileges assigned to the data entry staff and administrative staff; these privileges are outlined in detail in the OTIS Data Management Guide, Data Entry standard operating procedure (SOP), and supplements to these guides. An audit log is built into the database to archive all such entry edits.

Hard copies of patient files and subject signed consent forms will be kept in a locked cabinet under the supervision of the study investigators. Data collection and validation procedures will be detailed in appropriate operational documents.

## **7.7 Data analysis**

All analyses will be performed by the OTIS Research Center.

### **7.7.1 Analysis software**

All summaries and statistical analyses will be performed using the current version of open source statistical programming language R and StatXact.

### **7.7.2 Analysis variables**

#### **7.7.2.1 Outcome classification for the primary outcome – major structural defects**

The method for classifying major structural defects for purpose of analysis has been described by the study investigators and the OTIS Research Group ([CDC, 2017](#); [Chambers et al, 2001](#)) and has been used in previous studies conducted by OTIS.

### 7.7.2.2 Inclusion criteria for the primary outcome – major structural defects

**Definition:** a major structural defect is defined as a defect that has either cosmetic or functional significance to the child (e.g., a cleft lip).

- **Classification of major defects** will be performed according to the CDC coding list (CDC, 2017) and applied equally across all cohorts in the study. Some major structural defects are known consequences of pregnancy events, such as premature delivery, and are therefore not directly due to drug exposure. For example, isolated patent ductus arteriosus or isolated inguinal hernia in an infant delivered before 36 weeks' gestation are considered consequences of prematurity, and therefore, using CDC coding criteria, none of these defects are counted as major structural defects. Other structural defects, such as club foot or cranial synostosis, could be due to position of the infant in the uterus or could be primary defects initiated earlier in pregnancy. In most cases, it is not possible to know the true onset or etiology of the defect. Therefore, using CDC coding criteria, these anomalies are counted as major structural defects uniformly across all cohorts.
- Using CDC coding criteria, chromosomal anomalies are counted as major structural birth defects. Although it is unlikely that a drug exposure could cause a chromosomal defect, it is not impossible. These major structural defects are counted uniformly across all cohorts in the study. Similarly defects that are identified as due to genetic syndromes are coded uniformly across all cohorts.

This uniform coding reduces differences in outcome definitions between studies for a better interpretation of results in the event they are compared. Further, it allows for the use of the external comparator group compiled by the MACDP. It is anticipated that the occurrence of defects that are unrelated to drug exposure in the proposed study population will be non-differential across cohorts. Therefore, their inclusion, when indicated, represents part of the baseline risk for major structural defects in each cohort. This should not impact the risk estimates and measures of association.

With respect to known chromosomal defects or defects determined to represent a known genetic syndrome, a sensitivity analysis is planned, and outlined in the SAP that will exclude these defects.

- **Analysis subset:** for the primary outcome of major structural defects, the etiologically relevant window, with rare exceptions, is any exposure in the first trimester and the analysis subset in cohort 1 will be restricted to those with exposure to at least 1 dose of Mayzent from the 4th day post first day of to LMP prior to conception through the end of the first trimester. It is possible that some pregnant women in Cohort 1 could have exposure to Mayzent limited to the second or third trimester, and these would be considered separately. Duration and gestational timing of exposure to siponimod will also be considered.
- **Time period for identification:** major structural defects identified up to one year of age by the mother or the healthcare provider/medical record will be included in the primary analysis. Defects identified after that time frame will be described and considered separately.
- **Confirmation of defects:** independent confirmation of certain defects will be required. For example, a heart murmur thought to represent a ventricular septal defect

prior to 1 year of age will be included if it is confirmed as a heart defect by cardiac ultrasound. Similarly, a midline cutaneous marker at L2-L3 noted will be included as occult spinal dysraphism only if confirmed by appropriate imaging studies.

- ***Adjudication of major structural birth defects:*** major structural birth defects when reported are first classified by the OTIS study manager once all efforts have been made to obtain adequate information from the mother and infant's healthcare providers. All major structural birth defects are then reviewed in detail by Co-investigators on this study who are clinical teratologists and dysmorphologists/geneticists who are experts in birth defects. The Co-investigator is always blinded to the pregnancy exposure group at the time of the evaluation. If there is a discrepancy in the classification based on these two independent reviews, additional consultation is required for adjudication or classification. This is performed by a member of the Scientific Advisory Board or the Medical Director of the CDCs MACDP. These consultants are also blinded to exposure information at the time of the classification review. After this classification has been completed, at each annual interim and the final Scientific Advisory Board meeting for the study, all major structural birth defects are reviewed. The members of the Scientific Advisory Board, who are experts in major structural birth defects, as part of the review process, may ask for additional information regarding classification of major structural birth defects. However, at the time of the annual report review, the Scientific Advisory Board members are not blinded to exposure. The final adjudication of the classification of major structural defects is made through this multi-step process and all data presentations derived from the study will clearly describe the adjudication process.

#### **7.7.2.3 Exclusion criteria for the primary outcome – major structural defects**

- Defects will be excluded based on criteria outlined in the CDC coding list as outlined in [Section 7.7.2.2](#).
- ***Time period for identification:*** structural defects ascertained after 12 months of age will not be included in the primary analysis, but will be considered separately in the context of a possible pattern.
- ***Defects identified in spontaneous abortions/miscarriage, stillbirths or elective terminations/abortions:*** defects identified by prenatal ultrasound or examination of the products of conception following elective or spontaneous abortion/miscarriage or stillbirth will not be included in the primary analysis of the primary outcome due to potential bias involved in non-uniform use of prenatal diagnosis and pathology evaluation for all abortuses; however, these defects will be included in the additional analysis of the primary outcome that includes all defects in the numerator over all pregnancies enrolled in the prospective cohort with known outcome in the denominator (excluding lost-to-follow-up).

#### **7.7.2.4 Outcome classification for secondary outcomes**

- ***Spontaneous abortion:*** spontaneous abortion/miscarriage is defined as non-deliberate fetal death which occurs prior to less than 20.0 weeks post-LMP.
- ***Analysis subset:*** the analysis subset for the secondary outcome of spontaneous abortion will be restricted in Cohort 1 to those who were exposed to any dose from

the 4th day post first day of LMP prior to conception to 20 weeks' gestation and enrolled prior to 20 weeks' gestation. The analysis subset for cohorts 2 and 3 will be restricted to those who enrolled prior to 20 weeks' gestation.

- **Stillbirth:** stillbirth is defined as non-deliberate fetal death anytime in gestation at or after 20 weeks post-LMP.
- **Elective termination:** elective termination/abortion is defined as deliberate termination of pregnancy at any time in gestation. Reasons for elective abortions are captured and are classified as due to medical reasons or social reasons.
- **Premature delivery:** premature delivery is defined as live birth prior to 37.0 weeks gestation as counted from LMP (or calculated from first-trimester ultrasound-derived due date if last menstrual period uncertain or more than 1 week discrepant). Elective caesarian deliveries or inductions prior to 37.0 completed weeks will be considered separately.
- **Preeclampsia / eclampsia:** preeclampsia or eclampsia reported by maternal interview with confirmation in medical record or report by medical record only is captured.
- **Small for gestational age:** small for gestational age is defined as birth size (weight, length or head circumference) less than or equal to the 10th centile for sex and gestational age using standard pediatric CDC growth curves for full term or preterm infants (CDC, 2000; Olsen et al., 2010).
- **Minor structural defects:** a minor structural defect is defined as a defect which has neither cosmetic nor functional significance to the child (e.g., complete 2,3 syndactyly of the toes). Minor structural defects will be identified only through the study dysmorphology examination for live born infants using the study-specific checklist.
- **Postnatal growth deficiency:** postnatal growth deficiency is defined as postnatal size (weight, length or head circumference) less than or equal to the 10th centile for sex and age using National Center for Health Statistics (NCHS) pediatric growth curves, and adjusted postnatal age for premature infants if the postnatal measurement is obtained at less than one year of age (CDC, 2000).
- **Screening of Developmental Milestones:** one or more domains scored as abnormal on the Ages and Stages Questionnaire completed by the mother when the infant is approximately one year of age will define achievement of developmental milestones.
- **Serious or Opportunistic Infections:** serious or opportunistic infections are defined as any one or more diagnoses of tuberculosis, x-ray proven pneumonia, neonatal sepsis, meningitis, bacteremia, invasive fungal infection, pneumocystitis, septic arthritis, osteomyelitis, abscess (deep tissue), and infections requiring hospitalization identified in live born infants up to one year of age.

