#### **7.2.2.1 Inclusion criteria for core prospective study**

Participants must meet all the criteria listed under the respective cohorts to enroll in that particular cohort of the registry:

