#### **Cohort 1: Siponimod-Exposed Cohort**

1. Pregnant women
2. Diagnosed with MS, with the indication validated by medical records when possible
3. Exposure to siponimod for the treatment of MS, for any number of days, at any dose, and at any time from the 4th day post the first day of LMP prior to conception up to and including the end of pregnancy
4. Agree to the conditions and requirements of the study including the interview schedule, release of medical records, the dysmorphology examination of live born infants, and the Ages and Stages Questionnaire (ASQ) in live born children

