### **7.2.2.4 Analysis populations**

The Registry will collect and follow-up on reports of all types (i.e., retrospective, exposure after first trimester only, off-label indication, etc.: see [Section 7.2.2.3](#)) involving pregnancy exposure to siponimod; however, the core of the Registry will be a prospective cohort study designed to ascertain and follow-up on pregnancy exposures to siponimod and to compare these outcomes to 2 internally-generated comparison groups and one external comparison group (Metropolitan Atlanta Congenital Defects Program, or MACDP).

- Comparison Group 1 consisting of diseased-matched pregnant women who have not been exposed to siponimod at any time from the 4th day post first day of LMP prior to conception up to and including the end of current pregnancy. This will be the primary comparison group.
- Note that this cohort will be common between this study and the Kesimpta-OTIS pregnancy registry sub-study (OMB157G2403). The first 125 eligible pregnancies after OMB157G2403 protocol approval will be eligible for inclusion in both studies.
  - Comparison Group 2 consisting of pregnant women who contact the study directly or who are referred to the study, and who do not have MS, have not been exposed to a known human teratogen, and have not taken siponimod in pregnancy. This will be a secondary comparison group.
- Note that this cohort will be common between this study and the Kesimpta-OTIS pregnancy registry sub-study (OMB157G2403). The first 125 eligible pregnancies after OMB157G2403 protocol approval will be eligible for inclusion in both studies.

Based on previous OTIS experience, it is estimated that Comparison Group 2 will be similar to the exposed and primary comparison group on key demographics such as maternal age, socioeconomic status and race/ethnic distribution. However, differences between the cohorts for these demographic factors will be monitored in the annual interim reports and, should they occur, will be addressed in future recruitment efforts and in the statistical analysis phase of the study through methods such as adjustment (to be detailed in the SAP).

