**Table 7-1 Variables**

Variable	Role	Data source(s)	Operational Definition
Exposure to siponimod	Exposure	Maternal report Medical record	Maternal report of exposure to siponimod of at least one dose any time from 4 th days post first day of LMP prior to conception up to and including the end of pregnancy. Confirmation of exposure with medical records.
Dose of siponimod	Exposure	Maternal report Medical record	Dose of siponimod mg per day (maternal report and confirmation with medical records).

Variable	Role	Data source(s)	Operational Definition
Duration of siponimod use	Exposure	Maternal report Medical record	Weeks of siponimod use in pregnancy (maternal report and confirmation with medical records).
Indication	Exposure	Maternal report Medical record	Indication for use of siponimod (maternal report and confirmation with medical records).
Gestational age at time of initial exposure to siponimod	Exposure	Maternal report Medical record	Gestational age at the time of initial exposure to siponimod (maternal report and confirmation with medical records).
Major structural birth defect	Outcome – primary	Maternal report Medical record OTIS investigator review Dysmorphology Evaluation	The Registry adopts the term “major structural defect” (i.e., birth defect) for an abnormality usually referred to as a “congenital abnormality” and defines major structural defect as follows:  Any major structural or chromosomal defect defined and classified, using the CDC Metropolitan Atlanta Congenital Defects Program (MACDP) classification of birth defects ( CDC 2017 ).(including any intervention to correct the structural defect and its outcome) in any pregnancy including those ending in a live born infant or a pregnancy loss.
Minor structural defect	Outcome - secondary	Dysmorphology Evaluation	A defect which occurs infrequently in the population but which has neither cosmetic nor functional significance to the child and is identified using a study related checklist incorporated into the study dysmorphology examination of live born infants.
Spontaneous abortion	Outcome - secondary	Maternal report Medical record	Non-deliberate embryonic or fetal death that occurs prior to 20.0 weeks’ gestation.

Variable	Role	Data source(s)	Operational Definition
Stillbirth	Outcome - secondary	Maternal report Medical record	A non-deliberate fetal death that occurs at or after 20.0 weeks' gestation but prior to delivery.

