### **7.7.3.1.2 Analyses of secondary outcomes**

The analysis of spontaneous abortion (SAB) and stillbirth: Only those subjects who are enrolled prior to 20 weeks of gestation are eligible for the analysis of SAB. Since they are not followed from gestational age zero, survival analysis methods will be used to handle left truncation, as well as right-censoring when a subject is lost-to-follow-up prior to 20 weeks' gestation. Left-truncated Kaplan-Meier estimate at 20 weeks' gestation will be used to estimate the SAB rate in each of the cohorts (Tsai et al, 1987). The Cox proportional hazards regression models incorporating left truncation will be used to estimate the hazard ratio (HR) of different cohorts, as well as to obtain the 95% CIs. Stillbirth will be analyzed in a similar fashion. To account for potential confounding, PS methods described above will be applied, where regression adjustment will be used with the Cox model to obtain the adjusted HR.

The analysis of premature delivery: Only those subjects who are enrolled prior to 37 weeks of gestation are eligible for the analysis of premature delivery. These data will be analyzed similarly to SAB, as described above, using survival analysis methods to handle possible right-censoring.

The following will be considered binary endpoints: preeclampsia/eclampsia, small for gestational age (SGA) at birth in weight, height and head circumference, respectively, and growth deficiency at about one year of age in weight, height and head circumference respectively. The analysis of each of these outcomes will be similar to the analysis of the primary outcome, based on all pregnancies resulting in live born infants excluding twins or higher order multiples.

Multiple births will be included in the analyses of minor structural defects, ASQ, and serious or opportunistic infections. These outcome variables will thus likely contain correlated data due to twins or higher order multiples, and the generalized estimating equations (GEE) approach will be used (Liang and Zeger, 1986, Diggle et al, 2002).

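### The exposure rules for spontaneous abortion and preterm delivery do not require the first dose to precede enrolment, so any later starter analysed in Cohort 1 credits siponimod with event-free time

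*Protocol*

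**What the plan says.** - **Entry to Cohort 1 (7.2.2.1).** The criterion is "Exposure to siponimod for the treatment of MS, for any number of days, at any dose, and at any time from the 4"th day after the LMP until pregnancy ends. Table 7-1 defines the exposure variable over the same span: "Maternal report of exposure to siponimod of at least one dose any time from 4"th day onward. The lead-in to the criteria reads "Participants must meet all the criteria listed under the respective cohorts to enroll in that particular cohort of the registry".
- **Spontaneous abortion (7.7.2.4).** The subset "will be restricted in Cohort 1 to those who were exposed to any dose from" day 4 after the LMP to 20 weeks, and enrolment must be before 20 weeks. For the comparators, "The analysis subset for cohorts 2 and 3 will be restricted to those who enrolled prior to 20 weeks".
- **Cohort 2 (7.2.2.2).** Siponimod exposure up to the end of the pregnancy excludes a woman.
- **Model (7.7.3.1.2).** Cohorts are compared by Cox regression with left truncation, because women are not observed from gestational age zero. Stillbirth and premature delivery are analysed in a similar way. For the latter, "Only those subjects who are enrolled prior to 37 weeks of gestation are eligible for the analysis of premature delivery". Neither has an exposure window of its own.
- **Women exposed only late.** Section 7.7.2.2 says some Cohort 1 women "could have exposure to Mayzent limited to the second or third trimester, and these would be considered separately". Section 7.2.2.4 says the Registry will follow "reports of all types (i.e., retrospective, exposure after first trimester only, off-label indication, etc" and points to 7.2.2.3. The eligibility list there names only unapproved indication and retrospective reports.

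**The concern.** Enrolment is expected at 7–10 weeks on average (7.5.1), and exposure is updated at later interviews, so a first dose after enrolment can be recorded. If such a woman is analysed in Cohort 1 with follow-up from enrolment, the interval before her first dose counts as exposed. She must still have been pregnant at the dose, so that interval cannot contain her event. For premature delivery the extreme case is a first dose at or after 37.0 weeks, which makes her an exposed non-event by construction.

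The Cohort 2 exclusion pushes the same way. Removing women because of a later dose removes only women whose pregnancies lasted long enough to receive it.

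This is immortal-time bias. In a safety study it errs toward reassurance, and it affects outcomes that have their own rows in Table 7-4.

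**Working it through.** **Does the text admit a first dose after enrolment?** Two passages pull apart.

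1. The lead-in to 7.2.2.1 requires the criteria to be met in order to enrol. Read strictly, the dose precedes enrolment, and left truncation at enrolment then leaves no immortal time.
2. The subset rule in 7.7.2.4 requires both a dose by 20 weeks and enrolment before 20 weeks. If the dose always preceded enrolment, the second condition would imply the first. The dose limit has a function only if a first dose can follow enrolment. The Cohort 2 exclusion also runs to the end of pregnancy, which cannot be known at enrolment.

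The protocol does not settle which reading governs.

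**Plan's own figure.** Table 7-4 gives, for spontaneous abortion/stillbirth, 259 per group, 10% in the comparator, relative risk 1.9 and 80% power. Exact enumeration of the two-sided Fisher test for 19% versus 10% gives 80.2%. The figure reproduces and is not in dispute.

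**Size for spontaneous abortion.** From the protocol: enrolment at 7–10 weeks, a 10% baseline loss rate (stated for spontaneous abortion and stillbirth combined) and a horizon of 20 weeks. Assumed: a share f of Cohort 1 first dosed after enrolment, first dose uniform between enrolment and 20 weeks, and a hazard that is either constant or declines as exp(−0.25 × weeks).

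Hand approximation with entry at 8.5 weeks (window 20 − 8.5 = 11.5 weeks) and a drug with no effect. Let q be the average fraction of the window's hazard that remains after first dose. The apparent ratio is about 1 − f(1 − q).

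- Constant hazard: q = 0.5, so the ratio is 1 − 0.5f.
- Declining hazard: exp(−0.25 × 11.5) = 0.0564. The average of exp(−0.25x) over the window is (1 − 0.0564)/2.875 = 0.328. Then q = (0.328 − 0.0564)/(1 − 0.0564) = 0.288, so the ratio is 1 − 0.712f.

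A simulated left-truncated Cox model (400,000 women per group, entry uniform at 7–10 weeks) agrees:

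| f | By hand, constant / declining | Simulated, true HR 1.0, constant / declining | Simulated, true HR 1.9, constant / declining |
|---|---|---|---|
| 5% | 0.975 / 0.964 | 0.97 / 0.97 | 1.86 / 1.83 |
| 10% | 0.950 / 0.929 | 0.95 / 0.93 | 1.80 / 1.74 |
| 20% | 0.900 / 0.858 | 0.90 / 0.85 | 1.72 / 1.60 |

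At f = 0 the simulated null is 1.01 / 0.99, so simulation error is about 0.01. Entering these women at first dose returns about 1.0 and 1.9 throughout. The simulated comparator was left intact, so any further effect of the Cohort 2 exclusion is not included.

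**Size for premature delivery.** Assumed: 10% baseline risk, with a hazard rising from 24 to 37 weeks. With true HR 1.0 and f = 5%, 10%, 20%, first doses spread over 12–39 weeks give 0.99, 0.98, 0.97. First doses spread over 28–39 weeks give 0.97, 0.95, 0.91. With true HR 1.9 and f = 10%, the two patterns give 1.88 and 1.79.

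**The case against.** The best defence is the lead-in to 7.2.2.1. If exposure must exist at enrolment, the span to the end of pregnancy merely allows for enrolment at any gestational age, and the 20-week dose limit is redundant drafting. No section says that a woman enrolled unexposed and dosed later is moved into Cohort 1. This stands as far as it goes: a reader might infer that the protocol assigns such women to Cohort 1 from enrolment, and it does not say so. What remains is that it does not rule this out, and its subset rule makes most sense if it happens.

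Several stronger readings also fail.

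- **That late exposure itself causes bias.** A late first dose before enrolment adds no pre-dose time. First doses after 20 weeks are already outside the spontaneous abortion subset.
- **That a dose could follow a stillbirth.** Exposure must occur by the end of the pregnancy, so it cannot.
- **That preeclampsia needs a matching rule of dose before diagnosis.** It is a binary endpoint, and diagnosis does not end the pregnancy. Such a rule would remove cases from the exposed group and keep late-dosed non-cases, which lowers the exposed rate.
- **That 7.2.2.4 excludes women exposed only late.** It lists the reports to be collected. Only its grouping and its pointer to 7.2.2.3 sit badly with the Cohort 1 criterion.

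The share is unknown, and 7.9 expects exposure in unintended pregnancies, which suggests that most first doses precede enrolment. Coding of time-dependent exposure could also sit in the SAP. The subset rule and the Cohort 2 exclusion, however, are fixed in the protocol.

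**Conclusion.** The concern holds in conditional form. Followed literally, the exposure rules allow a dose after enrolment to make a woman exposed, and the stated comparison of cohorts would then count her event-free pre-dose time as exposed. The direction is toward an apparently safer drug. For spontaneous abortion a true hazard ratio of 1.0 would appear as about 0.97 at a 5% share, 0.93–0.95 at 10% and 0.85–0.90 at 20%. Premature delivery is usually less affected. With no such women there is no bias. The shares, dose timing and hazard shapes are assumptions, because the protocol gives none of them. The documents do not support the inference that the registry's estimates will be materially biased, since the affected share may be very small. The point merits a change because the ambiguity is real, the error would favour reassurance, and the remedy is cheap.

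**What to change.** 1. In 7.7.2.4 and 7.7.3.1.2, for spontaneous abortion, stillbirth and premature delivery, start exposed follow-up at the later of enrolment and first dose within the exposure window.
2. Count earlier enrolled time as unexposed through a time-dependent exposure. Alternatively, censor Cohort 2 women at first dose instead of excluding them because of a later one.
3. For premature delivery, count only a first dose before 37.0 weeks as exposure.
4. State in 7.2.2 how a woman first dosed after enrolment is classified.
5. Separately, reconcile the mention of exposure only after the first trimester in 7.2.2.4 with the Cohort 1 criterion, 7.2.2.3 and 7.7.2.2.

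The cost is wording. Exposure dates and gestational age at first exposure are already collected, and the planned Cox model already handles delayed entry. The only loss is a small amount of exposed person-time.
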